Patient-reported views on AV access outcomes (Appendix B). Pain at the AV access site during access cannulation will be assessed using the VDS or mAPS. Using VDS, pain will be categorized into four intensity levels: absent/no pain, mild pain, moderate pain, and severe pain/pain as bad as could be/extreme pain. Patients' satisfaction with the vascular access will be assessed with the SF-VAQ. Pain at the AV access site will be assessed as acute pain and chronic pain. Acute AV access pain (evaluated with VDS or mAPS) will be assessed as pain experienced during AV access cannulation; the average score obtained at 3 consecutive access cannulation sessions (initial assessment being done with the first cannulation) will be used for analysis. Chronic AV access pain will be assessed as part of the physical symptom domain with SF-VAQ.

TCVC-related outcomes: infectious (e.g., catheter exit site infection, tunnel infection, catheter-related bacteremia) and non-infectious (e.g., catheter malposition, mechanical dysfunction, catheter migration, venous thrombosis, pneumothorax, arterial puncture, hemothorax).

Clinical outcomes related to hospital admissions observed during the study period will be recorded and will include the main admission diagnosis and length of hospitalization.

All deaths that occur during the study period will be recorded and classified into six categories (Appendix E), and sub-classified as to whether death was access-related. The cause of death will be determined by the patient's primary nephrologist and/or primary doctor according to usual practice.

Analytical Plan

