Recruitment will be determined as the proportion of people meeting inclusion criteria who ultimately consent to randomization. We aim to consent $\geq 70\%$ of those eligible. Protocol adherence is based on the ability to undergo a graft or fistula surgery within 90 days of randomization, which we aim to attain in $\geq 70\%$ of participants. Outcomes of quality of life stratified by the type of first AV-access strategy. Changes in grip strength, pain related to the access (acute and chronic pain), patient's satisfaction with the access, changes in the level of independence (ADLs and IADLs) and HRQoL—will be compared between the two arms, with baseline (preoperative) assessments used as reference.

Subject Recruitment Methods

Clinical records of Wake Forest Nephrology practice, including WFOPD facilities, WFBMC nephrology outpatient clinics, and WFBMC nephrology inpatient service will be reviewed for eligibility. Study participants will be older adults of age ≥ 65 years with a diagnosis of incident ESKD or have advanced CKD expected to require HD initiation within 90 days of screening who meet the following additional inclusion criteria: (1) use a TCVC for HD, (2) did not undergo surgical creation of an AV access in the past, (3) are medically eligible to undergo surgery for AV access placement, and (4) are surgically eligible to undergo surgical placement of AVF and AVG. Medical eligibility for surgical placement of AV access will be determined as part of standard of care for patients with ESKD. In clinical practice, this aspect takes in consideration patient's clinical prognosis (e.g., unlikely to recover kidney function, medically stable to undergo surgical placement of AV access, anticipated life expectancy ≥ 9 months) and goals of care (HD is the intended long-term modality of treatment). Surgical suitability for placement of AV access, AVF and AVG, will be determined as part of standard of care by the vascular surgeon. To make this determination, the vascular surgeon will use the results of the ultrasound vascular mapping of both upper extremities. Patients who meet all the eligibility criteria will be approached by the vascular access coordinator, study coordinator, and/or PI for explanation of study participation.

Human Subjects Protection

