This study poses **moderate risks** to the study participants. The potential participants for this study have already been determined to need an AV access for chronic HD. This study plans to randomize the participants into two groups; each group will undergo surgical placement of one of the two types of AV access, fistula (forearm or arm) or AVG (forearm or arm), respectively. All interventions, procedures and complications will be treated and followed by their nephrologist as standard of care. Postoperative evaluation of AV access development will follow according to usual clinical practice for each individual. The patients are examined at the outpatient dialysis unit on a regular basis by the nephrologist, physician assistant, and nurses with experience in vascular access assessment. Timing of AV access cannulation and TCVC removal/reinsertion will be determined by patient's nephrologist. Any abnormalities that relate to the AV access including changes on physical examination (such as extremity edema; collateral veins; alterations in the pulse, thrill, or bruit of the fistula or graft; signs and symptoms indicative of limb ischemia) or problems noted during the dialysis session (such as inability to maintain prescribed blood flow rates, abnormal venous and/or arterial access pressures, prolonged bleeding at the end of dialysis, unexplained decrease in dialysis clearance) will be addressed as directed by patient's nephrologist according to standard practice. Vascular access procedures that may be performed on the AV access following surgical placement (such as fistulogram, thrombectomy, angioplasty, stent placement, ligation of collateral veins, access ligation, fistula superficialization) will also be directed by the patient's nephrologist and vascular surgeon according to standard practice.

All the assessments of upper arm muscle strength, AV access pain, level of independence, and patient reported views on vascular access and quality of life will be gathered either at participant's dialysis session or at regular physician office visit. Evaluation of acute AV access pain will be performed at the beginning of dialysis session. There will be no medical visits and no blood collections done exclusively for this study.

Informed Consent

Signed informed consent will be obtained from each subject by the study coordinator, a study team member, the vascular access coordinator, or the PI. The participant will have

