Appendix C: Schedule of Assessments

Schedule of assessments						
Assessment	Enrollment	Week 1 or 2 after AV access placement	Week 3 after AVG placed or Week 4 after AVF placed	Week 5 or 6 after first AV access cannulation	Week 24 or 25 of AV access use	Week 24 or 25 after AV access placement if primary AV access failure
Grip strength	√	√	Evaluation at DAG to assess AV access development and suitability for cannulation	√	√	√
4MGS	√			√	√	√
VDS or mAPS		√		√	√	√
SF-VAQ		√		√	√	√
ADLs and IADLs	√				√	√
KDQOL-SF 1.3.	√				√	√
Qualitative Study Interview						
AV, arteriovenous; 4MGS, four meter gait speed; VDS, Verbal Descriptor Scale; mAPS, Modified Abbey Pain Scale; SF-VAQ, Short-form vascular access questionnaire; ADLs, Activities of daily living; IADLs, Instrumental ADLs; KDQOL-SF, Kidney Disease Quality of Life Short-form. The Qualitative Study Interview will be performed on a maximum number of 10 subjects who have been enrolled in study >6 months and have had AV access surgery and are still currently enrolled in study either during a study visit or before the subject's dialysis treatment at their respective dialysis center.						

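### Access pain and satisfaction fall under a preoperative reference that the schedule does not collect, and the three-session cannulation-pain variable has no entry in Appendix C

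*Combined protocol and SAP*

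**What the plan says.** The Analytical Plan names the patient-centred outcomes in one sentence: changes in grip strength, access pain (acute and chronic), satisfaction with the access, and changes in independence and HRQoL. It ends by saying that these "will be compared between the two arms, with baseline (preoperative) assessments used as reference". For the method, the same section names only robust regression and non-parametric comparisons.

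The subsection on patient-reported views defines acute pain as pain during cannulation of the AV access, scored with VDS or mAPS, and states that "the average score obtained at 3 consecutive access cannulation sessions (initial assessment being done with the first cannulation) will be used for analysis". It adds: "Chronic AV access pain will be assessed as part of the physical symptom domain with SF-VAQ". Human Subjects Protection gives the moment of scoring: "Evaluation of acute AV access pain will be performed at the beginning of dialysis session".

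Appendix C, which the protocol presents as the summary of the schedule, leaves the enrollment cell empty for VDS/mAPS and for SF-VAQ. Both rows are ticked at the same four time points: "Week 1 or 2 after AV access placement"; "Week 5 or 6 after first AV access cannulation"; "Week 24 or 25 of AV access use"; and, for participants with primary access failure, "Week 24 or 25 after AV access placement". Grip strength, ADL/IADL and KDQOL-SF are ticked at enrollment.

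**The concern.** Read plainly, the closing clause of the Analytical Plan sentence governs the whole list, so it asks for a preoperative reference that is not scheduled for pain or satisfaction. The form of comparison for those outcomes would then have to be settled after the data are in.

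Two related matters follow. First, staff who work from the Appendix C table would not see the three cannulation sessions that feed the acute-pain variable, and a score missed at a first cannulation cannot be recovered. Second, that variable is defined only in participants who reach cannulation. Background, Rationale and Context expects fistulas to fail more often than grafts and to take longer to develop, so the cannulated groups are likely to differ between arms in more than access type. If the result were presented as an ordinary randomised comparison, it could mislead the design of the larger trial.

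**Working it through.** The plan gives no figure to reproduce on this point. The check sets the analysis sentence against Appendix C, row by row.

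| Outcome in the Analytical Plan | Instrument | Enrollment tick | First tick |
|---|---|---|---|
| Grip strength | Dynamometer | Yes | Enrollment |
| Acute access pain | VDS/mAPS | No | Week 1 or 2 after placement |
| Chronic access pain | SF-VAQ, physical symptom domain | No | Week 1 or 2 after placement |
| Access satisfaction | SF-VAQ | No | Week 1 or 2 after placement |
| Independence | ADL/IADL | Yes | Enrollment |
| HRQoL | KDQOL-SF | Yes | Enrollment |

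**Reference.** There are five instrument groups (grip, VDS/mAPS, SF-VAQ, ADL/IADL, KDQOL-SF). Three have an enrollment value and two do not. Because SF-VAQ serves two outcomes, three of the six listed outcomes lack a reference. The rows line up with the six time-point columns, and other rows do carry enrollment ticks, so the blanks do not look like an extraction fault.

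**Could a preoperative value exist?** For acute pain, no. It is pain during AV cannulation, and the Inclusion Criteria require that no AV access was placed before. For SF-VAQ, a preoperative form completed by a participant on HD would rate the catheter. It could be asked, but it is not scheduled, and it would not describe the AV access.

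**Three-session variable.** VDS/mAPS is ticked in 4 of the 6 columns. None of the four is cannulation session 1, 2 or 3, so 0 of 3 sessions have an entry. The week 1 or 2 tick comes before the week 3 (AVG) or week 4 (AVF) check of readiness for cannulation, so it records access-site pain, which is how Appendix B describes the scale. The next tick is five or six weeks after the first cannulation and cannot stand in for a score that begins with it.

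**Who contributes.** Cannulation pain needs surgery and then cannulation. Even the week 1 or 2 scores need surgery. The plan's adherence target is at least 70% operated within 90 days. With 50 randomised, 0.70 × 50 = 35, so up to 15 could lack surgery by then with the target still met, although some may have it later.

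**Baseline as covariate or change score.** This applies to grip, ADL/IADL and KDQOL-SF. Assume equal variances s² at both times, correlation r and least squares; the documents give no r.

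- Residual variance of a change score: 2s²(1 − r)
- Residual variance with baseline as covariate: s²(1 − r²)
- Ratio: 2(1 − r)/(1 − r²) = 2/(1 + r)
- r = 0.5: 2/1.5 = 1.33; r = 0.8: 2/1.8 = 1.11; r = 0.9: 2/1.9 = 1.05
- Estimating the covariate slope costs a factor of about 1 + 1/(50 − 4) = 1.022, which leaves 1.31, 1.09 and 1.03.

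The ratio describes precision only. With randomisation, both approaches estimate the same arm difference without bias. Under the planned robust regression these figures are only a guide.

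**Last two columns.** One counts weeks from the start of access use. The other counts weeks from placement and applies only after primary failure. They have different time origins and cover different participants.

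**The case against.** The best defence concerns the sentence itself. It speaks of changes in grip, then names pain and satisfaction, then speaks again of changes in independence and HRQoL. If the first mention covered everything, the second would be redundant. On that reading the baseline applies exactly to the instruments ticked at enrollment, and there is no contradiction. This reading is plausible and may be what was meant. What remains is that the clause closes the whole list and no text exempts pain or satisfaction.

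A reader might infer that cannulation pain has no collection plan. The documents do not support that: the body fixes the instrument, the sessions, the starting point and the summary, and Human Subjects Protection says when in the session it is scored. The gap is in the summary table alone.

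A reader might cite the enrollment data list under Data Collection and Outcome Measure(s) as further proof, since it omits both instruments. It also omits ADL/IADL and KDQOL-SF, which Appendix C does tick at enrollment, so its silence shows nothing.

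A reader might also argue that a catheter-based SF-VAQ before surgery would be a useful reference, given the interest in moving from catheter to AV access. For catheter users that is a legitimate option, but the plan neither schedules nor describes it.

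Finally, the Analytical Plan analyses access failures as randomised and handles missing data under MAR. That does not settle this point. Cannulation pain in someone never cannulated is undefined, not missing.

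**Conclusion.** The point holds as a minor one. As worded and scheduled, the preoperative reference cannot be applied to VDS/mAPS or SF-VAQ (2 of 5 instrument groups, 3 of 6 listed outcomes), and the three cannulation sessions are absent from Appendix C. The acute-pain comparison is restricted to a post-randomisation subset and needs that label. The expectation that this subset differs by arm rests on the protocol's own background statement, not on data.

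Two further inferences should be resisted. The distance between the last two columns should not be expressed as a range of weeks: it depends on when access use starts, for which no latest date is given, and cannulation timing is left to the patient's nephrologist. Nor is week 1 or 2 a clean single visit for comparing SF-VAQ, because most participants on HD would then still be dialysing through the catheter.

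The gain from covariate adjustment depends on a correlation that the documents do not state. These outcomes are secondary to the feasibility aim, and neither the consent and surgery targets nor the enrolment of 50 rests on them.

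**What to change.** 1. In the Analytical Plan, limit the baseline clause to grip, ADL/IADL and HRQoL. Compare postoperative SF-VAQ and access-site VDS/mAPS between arms without a baseline, at the visits already in Appendix C. State which access the SF-VAQ rates at each visit, and that these scores exist only in participants who had surgery.
2. Add cannulation sessions 1 to 3 to Appendix C for VDS/mAPS. Report their mean by arm among cannulated participants, with the number cannulated, labelled as not protected by randomisation.
3. For grip, ADL/IADL and KDQOL-SF, state that the planned robust regression models the follow-up value with the enrollment value as a covariate, in place of a raw change score.
4. Report the last two columns of Appendix C separately by arm, with the number in each, and state their different time origins.

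The cost is one reworded sentence, a few lines of analysis text, one schedule entry and one line on the SF-VAQ form. No new measurements are needed: the three pain scores are already planned in the body, and the enrollment values are already scheduled.

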4. Did not undergo AV access placement in the past
5. Medically eligible to receive AVF or AVG placement as deemed by the treating nephrologist
6. Surgically eligible to receive either an AVF or an AVG
7. HD is the intended long-term modality of treatment for ESKD
8. Planning to remain within Wake Forest provided health care for at least 12 months

Exclusion Criteria

1. Presence of an AVF or AVG
2. Previous attempt(s) for AV vascular access placement
3. Native vasculature not suitable for placement of AV access
4. Imminent transplant planned (within 6 months)
5. Anticipated life expectancy <9 months

This study targets elderly population with advanced CKD and ESKD; therefore, the clinical scenario of when an elderly individual is not able to consent for himself or herself will not be uncommon. Because the study objectives will not be met without including these subjects, this study plans to enroll elderly subjects who are not able to consent for themselves. The foreseeable risks to these subjects in this study are low as is the negative impact. For elderly with impaired mental capacity, permission for study participation will be obtained from the subject's Legally Authorized Representative (LAR).

Sample Size

This pilot trial has the principal aim of testing the feasibility of randomizing initial AV access placement to an upper extremity AVG-first (intervention) or AVF-first (comparator) strategy in patients ≥ 65 years of age. For this goal, we plan to enroll 50 participants (25 per arm).

Interventions and Interactions

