Screening for potential participants will be performed in two stages. In the first stage, all patients ≥ 65 years old who have pre-dialysis CKD or have ESKD receiving chronic HD will be screened for eligibility. Of these patients, only those who did not have a previous AV access surgery and are considered for AV placement (according to goals of care established by the patient's nephrologist) will be maintained as potential participants and advanced to the second phase of screening pending determination of surgical eligibility for placement of upper extremity AVF and AVG. Ultrasound vascular mapping of both upper extremities to assess vascular anatomy is routinely performed pre-operatively at our institution. Arterial diameter of ≥ 2 mm and vein diameter of ≥ 2.5 mm at the site of AV anastomosis indicate suitability for AVF surgical creation.⁷ To complete the eligibility criteria, patients must have proper anatomy (in either upper extremity) for placement of AVF (forearm or arm) and AVG (forearm or arm). After written informed consent is obtained, participants will be allocated with equal probability to either a graft-first (intervention) or fistula-first (comparator) strategy. Allocation to AVG or AVF will be done using randomly permuted blocks of varying sizes to maintain balance between the groups.

Demographic and medical data will be collected from all participants, using direct patient interview and electronic medical records. Following randomization, collected data is derived from standard of care and from assessments specifically conducted as part of this study.

Study-specific assessments will include muscle strength (assessed with upper arm grip-strength test in each arm using a hand-held dynamometer)¹⁷, four-meter gait speed (4MGS)
¹⁸(HealthMeasures. NIH Toolbox training manual English version.

Available at: <http://www.healthmeasures.net/images/nihtoolbox/>

[Training-Admin-Scoring_Manuals/NIH_Toolbox_Training_ManualEnglish_9-25-12.pdf](http://www.healthmeasures.net/images/nihtoolbox/Training-Admin-Scoring_Manuals/NIH_Toolbox_Training_ManualEnglish_9-25-12.pdf)

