We will begin by examining descriptive statistics (means, standard deviations, minima, quartiles, maxima) and plots of the data (histograms and boxplots) to become familiar with the data and check for outliers. The proportion of people meeting each of the feasibility and protocol adherence endpoints with accompanying 95% confidence intervals (CI) will be calculated using skew-corrected score tests with a continuity correction. The maximum uncorrected error margin associated with the estimation of consent and surgery rates is 0.138, obtained at $p=0.5$. This suggests that CI around these estimates will be tight enough to provide meaningful guideline in the design of the larger trial. We will describe participant characteristics and evaluate reasons for protocol violations. We will calculate rates of dropout and other events, although we expect low numbers. Robust regression and non-parametric methods will be used for comparisons between randomized arms. The associations between pre-operative muscle strength (continuous or binary variable) with AV access primary outcome will be tested using logistic regression. The participants will be followed for a minimum of 12 months following index AV access placement. Participants who undergo AV access placement >90 days after randomization or who experience primary or secondary AV access failure will be analyzed as randomized in the intention-to-treat (ITT) analysis. Missing data will be handled under the missing at random (MAR) assumptions in compliance with an ITT protocol.²⁶ We will pay close attention to variables with higher rates of missingness, relative to others or display missingness patterns that deviate from the MAR assumptions since they could inform and guide the development of the larger trial. Results from the pilot analyses are likely to have high variability, but will provide valuable insight that will be considered in the design of a larger trial.

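### Changes in grip strength, ADL/IADL and quality of life are to be compared between arms, but the plan does not name the enrollment value as a covariate

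*Combined protocol and SAP*

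**What the plan says.** The last paragraph of the Analytical Plan lists the functional and patient-reported outcomes. It puts grip strength as a change, and then "changes in the level of independence (ADLs and IADLs) and HRQoL", and says that these "will be compared between the two arms, with baseline (preoperative) assessments used as reference". Whether the word for change also governs quality of life is grammatically loose, but the clause about baseline covers the whole list.

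The method comes earlier in the same section: "Robust regression and non-parametric methods will be used for comparisons between randomized arms". No model is written out and no covariate is named there or anywhere else.

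Appendix C schedules grip strength, gait speed, ADL/IADL and KDQOL-SF at enrollment and again at the late visits. A baseline covariate will therefore exist for each of them.

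The Sample Size section sets the context: "This pilot trial has the principal aim of testing the feasibility of randomizing initial AV access placement". Fifty participants are planned, 25 per arm. No effect size, power or precision is given for the functional or quality-of-life outcomes.

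**The concern.** A change score subtracts the whole baseline value, which fixes the baseline coefficient at 1. When the correlation between baseline and follow-up is below 1 (and the SDs are equal), the best coefficient is smaller, so subtraction over-corrects. This has two consequences. The arm difference is noisier than it needs to be. In addition, any chance difference between arms at baseline reappears with the opposite sign in the comparison of changes, through regression to the mean.

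Both matter more in a small trial. Allocation uses permuted blocks with no stratification factor named, so the design balances arm sizes and not baseline function. The plan itself warns that "Results from the pilot analyses are likely to have high variability", and it intends those results to inform a larger trial. The hypothesis under Objectives, that graft-first limits loss of upper-extremity function, rests on this family of outcomes, and on grip strength in particular.

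**Working it through.** **The plan's own figure.** The only precision figure in the documents is an error margin of 0.138 for the consent and surgery rates at p = 0.5. With n = 50, 1.96 × √(0.25/50) = 0.1386, which agrees apart from truncation. Nothing comparable is given for the outcomes at issue here.

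**Inputs.** 25 per arm (Sample Size) and equal allocation (Interventions and Interactions). The correlation r is not in the documents and is assumed to lie between 0.3 and 0.9. Also assumed: equal SDs at both times, a linear relation and full follow-up. Results are in SD units.

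**Formulas.**
- Variance of the arm difference, change scores: 2(1 − r) × 2/25.
- Variance of the arm difference, baseline as covariate: (1 − r²) × 2/25, times 1 + 1/(50 − 4) = 1.0217 for estimating the slope.
- Ratio of adjusted to change: (1 + r)/2 × 1.0217.
- SE of a chance baseline difference: √(2/25) = 0.283 SD, so a 95% range of ±1.96 × 0.283 = ±0.55 SD.
- Shift in the change-score difference given an imbalance d: −(1 − r) × d. The last column uses d = 0.283.

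| r | 2(1 − r) | 1 − r² | Ratio before slope cost | Ratio with slope cost | SE, change | SE, adjusted | Size of shift |
|---|---|---|---|---|---|---|---|
| 0.3 | 1.40 | 0.91 | 0.65 | 0.66 | 0.335 | 0.273 | 0.20 |
| 0.5 | 1.00 | 0.75 | 0.75 | 0.77 | 0.283 | 0.248 | 0.14 |
| 0.7 | 0.60 | 0.51 | 0.85 | 0.87 | 0.219 | 0.204 | 0.08 |
| 0.8 | 0.40 | 0.36 | 0.90 | 0.92 | 0.179 | 0.172 | 0.06 |
| 0.9 | 0.20 | 0.19 | 0.95 | 0.97 | 0.126 | 0.125 | 0.03 |

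For comparison, the SE when baseline is ignored altogether is √(2/25) = 0.283. At r = 0.5 change scores do no better than that, and at r = 0.3 they do worse.

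In terms of numbers, and before the slope cost, change scores would need 50 × 2/(1 + r) participants to match an adjusted analysis of 50. That is about 77, 67, 59 and 53 at r = 0.3, 0.5, 0.7 and 0.9.

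**Check by simulation** (4,000 trials with no true effect, 25 per arm). The variance ratio was 0.76 at r = 0.5 and 0.86 at r = 0.7. The slope of the change-score estimate on the baseline imbalance was −0.51 and −0.31, against about 0 for the adjusted estimate. The mean of both estimators was within 0.002 SD of zero.

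**Sensitivity to follow-up.** With 18 per arm analysed (an assumption), the SEs of the change scores rise by √(25/18) = 1.18, about 18%. The variance ratios barely move: 0.77 at r = 0.5 and 0.88 at r = 0.7.

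**The case against.** The strongest objection is that the plan does not exclude baseline adjustment. Using baseline as a reference could mean subtracting it, entering it as a covariate, or both, and robust regression can carry a baseline term. If change is regressed on arm and baseline, Y − B = a + bT + cB rearranges to Y = a + bT + (1 + c)B. For least squares and regression-equivariant robust methods, the arm coefficient b is then identical to that of the adjusted analysis. This stands. A reader might infer that the sponsor chose change scores over adjustment, and the text does not support that. It does not settle the matter in the plan's favour either: a two-sample rank test on changes fits the wording just as well and has no baseline term.

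A reader might also infer that the planned comparison is biased. It is not: randomization makes the change-score difference unbiased on average. The shift is conditional on the imbalance that happens to occur.

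Three further points stand in part. The size of the gain depends on a correlation that the documents do not give, and at r = 0.9 the gain is negligible. The formulas are for a linear model with equal variances, so they carry over only approximately to robust or rank methods and to bounded ADL/IADL scores. Finally, these are exploratory outcomes in a feasibility pilot.

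**Conclusion.** The point holds as a gap in specification with a clear preferred filling. The plan describes a comparison of changes and names no baseline covariate, although one is collected for grip strength, ADL/IADL and KDQOL-SF. On the ordinary reading the analysis gives up precision. Adjustment would cut the variance of the arm difference by about 34%, 23% and 13% at r = 0.3, 0.5 and 0.7, and by 8% and 3% at r = 0.8 and 0.9. Adjustment would also remove the conditional shift of up to about 0.20 SD per standard error of baseline imbalance over the range assumed. These figures rest on 25 analysed per arm, equal SDs, a linear model and the assumed r.

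It would be wrong to conclude that the trial's main result is at risk. The sample size, the two 70% targets and the stated margin of 0.138 all concern feasibility, and none of them depends on this choice. The change is worth making because it is nearly free and because the plan expects noisy estimates.

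**What to change.** Add to the Analytical Plan that, for grip strength, each KDQOL-SF scale, ADL and IADL (and gait speed if it is compared between arms), the arm difference is estimated by robust regression of the follow-up value on randomized arm and enrollment value. Specify rank ANCOVA for the bounded ADL and IADL scores. Report the adjusted difference with a 95% CI, and show change scores descriptively. Rank ANCOVA yields a test and not a natural interval, so say that the ADL/IADL difference and its interval come from the regression.

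Limit the sentence to outcomes that have an enrollment value. Appendix C shows none for access pain (VDS or mAPS) or for satisfaction (SF-VAQ), so the baseline clause needs separate wording for those two.

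The cost is a sentence or two of text. No assessment is added and the methods stay within those already named. The small downsides are one extra slope to estimate (about 2% in variance at N = 50) and the need to fix in advance the rank-based form for the bounded scales.
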